12.4.2 BMD in the Post-Treatment Follow-Up Period

Percent change from Baseline to Post-Treatment Follow-up Month 6, Post-Treatment Follow-up Months 7 – 11, and Post-Treatment Follow-up Month 12 will be summarized for each analysis group with descriptive statistics. There will be no statistical testing of Post-Treatment Follow-up BMD values.

The analysis of percent change in BMD will be repeated to include only the subset of subjects who had a Treatment Month 6 and a Post-Treatment Follow-up Month 6 scan. Similarly, this analysis will be repeated to include only the subset of subjects who had a Treatment Month 6 and a Post-Treatment Follow-up Month 12 scan.

Percent change from Baseline in BMD to each of the Post-Treatment visits will be summarized for each analysis group with frequencies and percentage for categories of BMD decrease: $\leq 0\%$, $> 0\% - \leq 1.5\%$, $> 1.5\% - \leq 3\%$, $> 3\% - \leq 5\%$, > 5% - < 8%, and $\geq 8\%$.

Cross-tabulations of the number and percentage of subjects in each of the previously noted categories of percent change from Baseline for the following:

- Treatment Month 6 to Post-Treatment Follow-up Month 6
- Treatment Month 6 to Post-Treatment Follow-up Month 12
- Final Treatment to Post-Treatment Follow-up Month 6
- Final Treatment to Post-Treatment Follow-up Month 12
- Post-Treatment Follow-up Month 6 to Post-Treatment Follow-up Month 12.

The subjects included in these analyses will be limited to those who had values at these time points.

As described above for the Treatment Period, continuous and categorical summaries of the Z-score and T-score at each time point during the Post-Treatment Follow-up Period will be provided.

Listings of subjects meeting the following thresholds during the Post-Treatment Followup period will be provided:

- Listing of subjects with bone decrease \geq 3% and T-score < -1.0 in the same region
- Listing of subjects with T-score ≤ -1.5 .

For the purposes of assessing post-treatment BMD recovery, the following summaries will be provided. The "recovery" statistic will be defined as

Recovery at post-treatment month $X = 100 \times ((\% \text{ change from baseline to final}) - (\% \text{ change from baseline to post-treatment month X}))/(% \text{ change from baseline to final}) i.e., it is the proportion of BMD decrease at the final treatment scan recovered at Post-Treatment Month X. For example, a subject who has a change of -2% at the end of treatment and has a change of -1% at Post-Treatment Month 6 will have a recovery value of 50% at Post-Treatment Month 6. This statistic is only defined for subjects who experience a decrease from baseline at final treatment.$

A continuous summary of recovery at each post-treatment visit will be provided including mean, standard deviation, median and a within-group 95% confidence interval. Additionally, the number and percentage of subjects in each of the following categories will be provided: < 0%, 0 - 25%, > 25 - 50%, > 50 - 75%, > 75 - 100%, > 100%.

A plot of the cumulative distribution function of recovery at Post-Treatment Month 6 and Post-Treatment Month 12 will be provided.

12.5 Vital Signs and Body Weight

Vital sign variables include pulse rate, sitting systolic blood pressure, sitting diastolic blood pressure, and oral body temperature.

Vital sign variables will be summarized with mean, median, standard deviation, minimum, and maximum by the four main groups as in Section 5.3.

Analyses of mean change from Baseline to each relevant visit during the Treatment Period in vital sign variables and weight will be performed by the four main groups as in Section 5.3.

The number and percentage of subjects who have PCS vital sign and weight values meeting the following criteria will be summarized by the six analysis groups as in Section 5.3. All increase/decrease is calculated from Baseline to a post-baseline visit in the Treatment Period.

The number and percentage of subjects who have a sustained PCS vital sign value and a listing of these subjects will be provided. A sustained PCS value is defined as 3 consecutive PCS values in the Treatment Period.

- Diastolic blood pressure
 - $\circ \leq 50 \text{ mmHg and} \geq 15 \text{ mmHg decrease}$
 - \circ > 90 mmHg and \geq 15 mmHg increase
 - $\circ \geq 100 \text{ mmHg}$
- Systolic blood pressure
 - $\circ \leq 90 \text{ mmHg and} \geq 20 \text{ mmHg decrease}$
 - $\circ \geq 140 \text{ mmHg and} \geq 20 \text{ mmHg increase}$
 - $\circ \geq 160 \text{ mmHg}$
- Pulse rate
 - $\circ \leq 45$ bpm and ≥ 15 bpm decrease
 - \circ > 100 bpm and \geq 15 bpm increase
 - $\circ \geq 120 \text{ bpm}$
- Weight
 - $\circ ~~ \geq 5\%~decrease$
 - $\circ \geq 7\%$ increase.

CODVIE Elagolix (ABT-620) M12-816 - Statistics

Elagolix (ABT-620) M12-816 – Statistical Analysis Plan Version 2.0 – 24 May 2018

Change in vital signs from Baseline to relevant Post-Treatment Follow-up visit(s) (Post-Treatment Month 1, Month 3, Month 6, Month 9, Month 12, and Final Visit) will be summarized by the four main groups as in Section 5.3 with descriptive statistics.

12.6 Endometrial Biopsy

The number and percentage of subjects in each category of endometrial biopsy results will be summarized at Baseline, Prior to Month 6, and Month 6 for each of the six analysis groups as in Section 5.3. If multiple assessments exist in a specific time window, all assessments will be displayed.

12.7 Pelvic Ultrasound and MRI

Analyses will be conducted separately for results obtained from TAU/TVU and MRI. The actual values and the change from Baseline to Month 3 (TAU/TVU only), Month 6, Follow-up Month 3 (TAU/TVU only), and Follow-up Month 6 will be summarized by the six analysis groups as in Section 5.3 with descriptive statistics.

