## 1.1 Protocol Amendment: Summary of Changes

### Previous Protocol Versions

Protocol	Date
Original	29 July 2016
Administrative Change 1	08 August 2016
Administrative Change 2	25 August 2016

The purpose of this Amendment is to:

- Update [Table 1](#), Visit and Assessment Windows to remove MRI from Post-Treatment Follow Up Period Month 6  
**Rationale:** *MRI is not required at Post-Treatment Month 6*
- Update Section [5.1](#) Overall Study Design and Plan, Visit Windows to clarify Treatment Period Visit schedule.  
**Rationale:** *Clarify the scheduling of visits in the Treatment Period is based on the date of the Day 1 Visit.*
- Update Section [5.3.1.1](#) Study Procedures, Mammogram to clarify when a mammogram is performed at the Premature Discontinuation Visit.  
**Rationale:** *A mammogram is only required at the Premature Discontinuation Visit if it has been approximately 12 months since the Screening mammogram was performed.*
- Update Section [5.3.3.2](#) Secondary Efficacy Variable to remove fibroid and uterine volume.  
**Rationale:** *This is included in other efficacy variables.*
- Update Section [5.4](#) Removal of Subjects from Therapy or Assessment to clarify when in the Study, surgical interventions and elevated liver enzymes constitute study withdrawal.  
**Rationale:** *Clarify which subjects require withdrawal during treatment and post-treatment follow up period.*

- Update [Appendix C](#) Study Activities – Treatment Period and Post-Treatment Follow-Up Period footnote for mammogram at the Treatment Period Premature Discontinuation Visit

**Rationale:** *To clarify when a mammogram is performed at the Treatment Period Premature Discontinuation Visit.*

- Update Section [5.3.1.1](#) Study Procedures, Endometrial Biopsy to remove the sixth paragraph

**Rationale:** *Sixth paragraph is a repeat of the text in the second paragraph and is not required*

- Update Section [5.4.1](#) Discontinuation of Individual Subjects to clarify Post-Treatment Follow-Up Period Visit schedule for subjects who prematurely discontinue

**Rationale:** *Clarify the scheduling of visits in the Post-Treatment Follow-Up Period is based on the date of the last dose of study drug for subjects who prematurely discontinue from study drug treatment.*

- Update Section [5.5.5](#) Blinding of Investigational Product to add time period AbbVie will remain blinded.

**Rationale:** *To clarify the time period AbbVie will remain blinded.*

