**Table 1. Visit and Assessment Windows**

Study Visit Windows	
Study Visit	Visit Windows
Treatment Period: Months 1 – 5	±4 days
Treatment Period: Month 6	–4 or +6 days
Post-Treatment Follow-Up Period: Months 1 – 12	±7 days
Assessment-Specific Windows for Treatment and Post-Treatment Period	
Study Visit/Assessment	Visit Windows
Treatment Period	
Month 3: Ultrasound, DXA Scan (if applicable)	±7 days
Month 6: Ultrasound, MRI (if participating in MRI subset) DXA Scan and Endometrial Biopsy	–15 or + 4 days
Post-Treatment Follow-Up Period	
Month 3: MRI (if participating in MRI subset)	–15 or +4 days
Month 6: Ultrasound, DXA Scan	–15 or +4 days
Month 12: DXA Scan	–15 or +4 days

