### **Magnetic Resonance Imaging (MRI) Subset:**

Subjects who participated in the MRI subset in the Pivotal Studies will continue to be included in the MRI subset in this study.

An MRI will be performed at the Month 6 or Premature Discontinuation Visit during the Treatment Period and at the Post-Treatment Follow-Up Month 3 Visit. Subjects who had an MRI performed in the past 3 months prior to prematurely discontinuing are not required to repeat the MRI at the time of Premature Discontinuation during the Treatment or Post-Treatment Follow-Up Period.

Assessments for the MRI include, but are not limited to the following:

- Fibroid volume in cubic centimeters (of 3 largest fibroids)
- Fibroid location
- Uterine volume in cubic centimeters
- Presence of adenomyosis (diffuse adenomyosis as the dominant condition versus focal)
- Presence of any concerning findings

Depending on the size of the uterus, MRI images of the abdominal cavity may need to be submitted to measure uterine volume and to assess for safety. It is recommended to follow standard of care when determining which anatomical sections are to be included in order to prevent incomplete views, thus leading to repeat procedures. Please refer to the Image Acquisition Guidelines for further details.

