Table 4 will be used for analyses of endpoints collected at Post-Treatment Month 1, 3, 6, 9, and 12 of the extension study (e.g., vital signs, clinical safety labs including chemistry, hematology, lipid panel and urinalysis, apolipoprotein A and B). Table 5 will be used for analysis of endpoints collected at Post-Treatment Month 3 and 6 of the extension study (e.g., TAU/TVU). Table 6 will be used for analysis of endpoints collected at Post-Treatment Month 3 of the extension study (e.g., MRI). Table 7 will be used for analysis of endpoints collected at Post-Treatment Month 6 and 12 of the extension study (e.g., BMD).

Table 4.Analysis Time Windows for Non-Bleeding Measurements Collected
at Post-Treatment Month 1, 3, 6, 9, 12

	Nominal Day (Study End Day)	Time Window (Study End Days)
Post-Treatment Month 1	28	> 3 - < 42
Post-Treatment Month 3	84	> 42 - ≤ 126
Post-Treatment Month 6	168	$> 126 - \le 210$
Post-Treatment Month 9	252	$> 210 - \le 294$
Post-Treatment Month 12	336	> 294

Table 5.Analysis Time Windows for Non-Bleeding Measurements Collected
at Post-Treatment Month 3 and 6

	Nominal Day (Study End Day)	Time Window (Study End Days)
Post-Treatment Month 3	84	> 28 - ≤ 126
Post-Treatment Month 6	168	$> 126 - \le 210$
Post-Treatment Months 7 – 12	266	> 210

Table 6.Analysis Time Windows for Non-Bleeding Measurements Collected
at Post-Treatment Month 3

	Nominal Day (Study End Day)	Time Window (Study End Days)
Post-Treatment Month 3	84	> 28 - ≤ 126
Post-Treatment Months 4 – 12	224	> 126

Table 7.Analysis Time Windows for Non-Bleeding Measurements Collected
at Post-Treatment Month 6 and 12

	Nominal Day (Study End Day)	Time Window (Study End Days)
Prior to Post-Treatment Month 6	84	$> 28 - \le 140$
Post-Treatment Month 6	168	$> 140 - \le 196$
Post-Treatment Months 7 – 11	252	$> 196 - \le 308$
Post-Treatment Month 12	336	> 308

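### SAP Section 12.7 puts its ultrasound-only label on follow-up Month 3 instead of follow-up Month 6, against the MRI schedule and SAP Table 6

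*SAP*

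**What the plan says.** SAP Section 12.7 opens with "Analyses will be conducted separately for results obtained from TAU/TVU and MRI". It then lists the visits at which actual values and changes from baseline are summarized. On treatment these are Month 3, marked as ultrasound only, and Month 6. In follow-up they are "Follow-up Month 3 (TAU/TVU only), and Follow-up Month 6". The last visit carries no qualifier, so it applies to both modalities.

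The protocol's MRI subset text (Section 5.3.1.1) reads "An MRI will be performed at the Month 6 or Premature Discontinuation Visit during the Treatment Period and at the Post-Treatment Follow-Up Month 3 Visit". Protocol Table 1 agrees. Its follow-up rows include "Month 3: MRI (if participating in MRI subset" and, for the later visit, "Month 6: Ultrasound, DXA Scan", with no MRI.

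SAP Section 7.4.3, which defines the analysis windows, also treats MRI as a Month 3 follow-up endpoint: "Table 6 will be used for analysis of endpoints collected at Post-Treatment Month 3 of the extension study (e.g., MRI".

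**The concern.** Section 12.7 is an operative instruction for a table. A programmer who follows it literally would drop MRI from the one follow-up visit at which MRI is scheduled and would set up an MRI summary at a visit where none is scheduled. The SAP would then be inconsistent with itself: MRI is summarized at follow-up Month 3 in the efficacy imaging sections and excluded there in the safety imaging section. What is at stake is whether one set of descriptive tables in an imaging subset is correct and traceable.

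**Working it through.** No sample size, power or error rate is involved, and the plan states no figure to reproduce. The check compares the schedule with the analysis text and then tests the windows.

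**Schedule against Section 12.7, follow-up period**

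| Source | Follow-up Month 3 | Follow-up Month 6 |
|---|---|---|
| Protocol 5.3.1.1, MRI subset | MRI | no MRI |
| Protocol 5.3.1.1, pelvic ultrasound | ultrasound | ultrasound |
| Protocol Table 1 (imaging entries) | MRI | ultrasound (with DXA) |
| Protocol Appendix C | ultrasound and MRI | ultrasound |
| SAP Table 5 (ultrasound windows) | yes | yes |
| SAP Table 6 (MRI windows) | yes | none |
| SAP 12.7 | ultrasound only | ultrasound and MRI |

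Appendix C also marks an MRI at premature discontinuation from follow-up, waived if one was done in the previous 3 months. SAP Section 3.0 says that the plan was built on Amendment 1, so the current protocol schedule is the one it should follow. The amendment summary gives the reason, "MRI is not required at Post-Treatment Month 6", but the comparison does not rest on it; the current text is enough.

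**Window check**

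- A study month is 28 days, so follow-up Month 3 is nominally Study End Day 3 × 28 = 84 and follow-up Month 6 is 6 × 28 = 168. Both match the nominal days in the SAP tables.
- Protocol Table 1 allows the follow-up Month 3 MRI from 15 days before to 4 days after: 84 − 15 = 69 and 84 + 4 = 88.
- The SAP Table 6 window for Month 3 is above 28 and up to 126. Days 69 to 88 lie wholly inside it, so the scheduled scans have a valid analysis window, yet 12.7 excludes them.
- A scan near Day 168 exceeds 126, so Table 6 places it in the Months 4 to 12 window. The Month 6 MRI summary that 12.7 requests therefore has no window to draw on.

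**Treatment-period half of the sentence**

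The ultrasound-only label on treatment Month 3 is correct, because on-treatment MRI is scheduled only at Month 6 or at premature discontinuation. The follow-up half appears to repeat that pattern, although in follow-up the MRI visit is Month 3.

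**What is still covered elsewhere in the SAP**

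- Section 11.3.5.1 analyses ultrasound and MRI separately and summarizes fibroid and uterine volume at post-treatment Month 3, and at Month 6 where applicable.
- Section 11.3.5.2 tabulates fibroid location at the same follow-up visits, without naming the modality.
- Section 11.3.5.3 covers adenomyosis, separately by MRI, at each relevant follow-up visit.
- Section 12.7.1 tabulates cyst percentages for treatment-period visits only, so the follow-up label does not touch that table.
- Section 12.7.2 summarizes change in endometrial thickness at relevant follow-up visits and sets no modality limit of its own.

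**The case against.** The strongest reply is that little is lost. The protocol's named MRI assessments are fibroid volume, fibroid location, uterine volume, adenomyosis and any concerning findings. Volumes and adenomyosis are planned by MRI at follow-up Month 3 in Section 11.3.5, and location is tabulated there too. The two subsections of 12.7 deal with ovarian cysts and endometrial thickness, which the protocol's MRI list does not name, although that list is not exhaustive and the SAP allows MRI readings of both. A programmer applying Table 6 would meet the conflict at once. All of this stands, and it limits the consequence to the general visit list that opens 12.7. It does not make that list right.

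A reader might infer three stronger things, none of which the documents support:

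- **That follow-up Month 3 MRI data are lost from the analysis.** Sections 11.3.5.1 and 11.3.5.3 still summarize them.
- **That every scheduled follow-up MRI is misallocated.** Table 6 windows these scans correctly, and 12.7 reassigns none of them.
- **That stray scans would fill a Month 6 MRI column.** Any MRI after Study End Day 126 goes to the Months 4 to 12 window, so under Table 6 the column would be empty. The accurate description of a Month 6 follow-up MRI is not scheduled, rather than not done, since a premature-discontinuation scan could fall near that time.

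**Conclusion.** The visit list in SAP Section 12.7 is wrong as written. It conflicts with the protocol's procedure text, Table 1 and Appendix C, and with SAP Table 6. The result is a descriptive summary that omits the scheduled follow-up Month 3 MRI and requests a Month 6 MRI summary with no scheduled scan and no window.

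The size is small. One section is affected, for the MRI subset only, and no hypothesis test, primary result, sample size or error rate changes. The severity is the lowest. The conclusion assumes that the unqualified follow-up Month 6 entry is meant to cover both modalities, which is the natural reading given the section's opening sentence and its use of the qualifier at other visits.

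**What to change.** In SAP Section 12.7, move the ultrasound-only qualifier from follow-up Month 3 to follow-up Month 6. The follow-up visits would then read: Follow-up Month 3, and Follow-up Month 6 (TAU/TVU only). Leave the qualifier on treatment Month 3 as it is. This brings the section into line with SAP Tables 5 and 6 and with the protocol schedule. The cost is one line of SAP text, with no new data and no change to any study procedure.

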12.7.1 Ovarian Cysts

The presence of ovarian cysts will be noted at Baseline and each relevant post-baseline visit in the Treatment Period and Post-Treatment Follow-up Period. Significant ovarian findings include complex ovarian cyst > 3.5 cm or simple ovarian cyst > 5 cm. The number and percentage of subjects with the pre-defined complex ovarian cysts and simple ovarian cysts will be summarized for each analysis group at each relevant visit in the Treatment Period.

For each TVU/TAU or MRI assessment, information for significant ovarian findings from the cysts assessment may be available for more than one cyst at more than one ovary location (left and/or right). For such assessments, the worst assessment based on the greatest of the three dimensions across the multiple cysts at the left and/or right ovary location within the same cyst type (i.e., simple or complex) will be included in the analyses/summary. Additionally, the subject with multiple cyst findings will be counted once in the numerator and denominator when reporting the number and percentage of

subjects in the relevant category of significant ovarian findings. A listing will include all results across multiple cysts findings from multiple assessments (where available) from subjects who have significant ovarian findings.

12.7.2 **Endometrial Thickness**

Analysis of change in endometrial thickness from Baseline to Month 3 and Month 6 in the Treatment Period will be performed.

In addition, the number and percentage of subjects with endometrial thickness of < 8 mm, \geq 8 mm and \leq 12 mm, > 12 mm and \leq 18 mm, and > 18 mm in the Treatment and Post-Treatment Follow-up Periods will be summarized by analysis group at each relevant visit in the Treatment Period.

Change in endometrial thickness from Baseline to relevant Post-Treatment Follow-up visit(s) will be summarized by analysis group with descriptive statistics.

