### **Adverse Events of Special Interest**

Adverse events of special interest in elagolix clinical studies include mood changing disorders (suicidality and depression), cutaneous adverse events, hot flush, ovarian-related events, BMD decrease and fractures, uterine bleeding and changes in serum lipids. In the completed Phase 2 studies in uterine fibroids, there was a higher percentage of women experiencing cutaneous/hypersensitivity events and hot flush with elagolix treatment compared with placebo. Adverse events of special interest are monitored continuously in all clinical studies.

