### **Pelvic Ultrasound: TAU and TVU**

Pelvic ultrasounds (TAU and TVU) will be performed at Treatment Period Month 3 and Month 6 and at Post-Treatment Follow-Up Period at Month 3 and Month 6 or at the time of premature discontinuation (if not performed within the past 2 months). Assessments for the pelvic ultrasound include, but are not limited to the following:

- Endometrial thickness
- Presence of abnormal endometrial appearance or endometrial pathology
- Presence of uterine fibroids
  - Number of uterine fibroids
  - Volume and location of the 3 largest fibroids
- Uterine volume in cubic centimeters
- Presence of ovarian cysts
  - Number
  - Size (cm)
  - Location (right or left ovary)
  - Simple versus complex
- Endometrioma > 3.5 cm longest diameter
- Solid ovarian lesions > 1.5 cm longest diameter

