#### **Ovarian Findings:**

During Treatment or Post-Treatment Follow-Up Periods, if the pelvic ultrasound shows a simple ovarian cyst > 5 cm or a complex ovarian cyst (including endometriomas) > 3.5 cm in longest diameter the findings should be documented as an adverse event if the Investigator considers them to be clinically significant.

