**6.1.1.3 Adverse Events of Special Interest**

Some adverse events, such as adverse events of special interest (AESI), such as rash/hypersensitivity, fracture, neuro-psychiatric (depression, mood swings, etc.), vasomotor symptoms (hot flush, night sweats) or serious adverse events. AbbVie may require additional information, including family history, to be collected and recorded in the eCRF.

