#### **8.1.8.7 Pelvic Ultrasound**

The number and percentage of subjects with complex ovarian cysts  $> 3.5$  cm, as well as the number and percentage of subjects with simple ovarian cysts  $> 5$  cm will be summarized for each treatment group at each time point. The change from baseline to

Month 6 in the Extension Study in endometrial thickness will be summarized for each treatment group.

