- Any serious AEs (SAEs) (by primary MedDRA SOC and PT, by PT)
- Any severe AEs (by primary MedDRA SOC and PT)

- Any SAEs reasonably possibly related to study drug (by primary MedDRA SOC and PT, by PT)
- Any SAEs leading to study drug discontinuation (by primary MedDRA SOC and PT)
- Any AEs of special interest as specified in Appendix M
- Any AEs leading to death (by primary MedDRA SOC and PT)

A listing by the four main analysis group as in Section 5.3 of treatment-emergent AEs with subject IDs will be generated. Listings of all treatment-emergent SAEs, AEs leading to death, and AEs leading to study drug discontinuation will be generated.

Summary of total number of hot flush and night sweat by subject-reported severity categories, summary of total number of hot flush and night sweat by maximum subject-reported severity, and summary of time to first onset of hot flush and night sweat will be provided. Listings of subjects associated with hot flush and night sweat will also be provided.

Post-Treatment Follow-Up Period

The Post-Treatment AEs will be summarized as follows:

- Any AEs by primary MedDRA SOC and PT
- Any SAEs by primary MedDRA SOC and PT.

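### SAP 12.7.1 plans no by-group count of large ovarian cysts at the two follow-up ultrasounds, although the protocol plans that count at every time point

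*SAP*

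**What the plan says.** **Schedule.** Protocol 5.3.1.1 (Pelvic Ultrasound: TAU and TVU) and Appendix C place scans at Treatment Months 3 and 6 and at Post-Treatment Months 3 and 6. Ovarian cysts are recorded by number, size, side and type.

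**Protocol analysis.** Under 8.1.8.7, the number and percentage of subjects with complex cysts > 3.5 cm, and with simple cysts > 5 cm, "will be summarized for each treatment group at each time point".

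**SAP analysis.** Section 12.7.1 uses the same two size limits and says that cyst presence is noted in both study periods. It then says that the pre-defined complex and "simple ovarian cysts will be summarized for each analysis group at each relevant visit in the Treatment Period". It adds a listing of all cyst results for subjects with significant ovarian findings, with no stated period limit. The parent section, 12.7, plans actual values and changes from baseline for imaging at visits that include Follow-up Months 3 and 6. It does not name cysts.

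**Adverse events.** For a cyst above either limit in either period, Protocol 5.3.1.1 (Ovarian Findings) says that "the findings should be documented as an adverse event if the Investigator considers them to be clinically significant". Protocol 3.2.2 includes in its events of special interest "hot flush, ovarian-related events, BMD decrease and fractures, uterine bleeding and changes in serum lipids". SAP 12.2.1 tabulates, for treatment-emergent events, "Any AEs of special interest as specified in Appendix M". The Appendix M table has no ovarian row.

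**The concern.** The SAP is narrower than the protocol on a safety summary, and it gives no reason. Protocol 8.1.8.7 does not leave the detail to the SAP, as Protocol 8.1.8.3 (laboratory data) and 8.1.8.4 (BMD) do. The SAP's list of changes from Version 1.0 does not mention the point.

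What is at stake is the post-treatment picture. General safety through the 12-month follow-up is among the design aims (Protocol 5.1), and pelvic ultrasound findings are a named safety variable (Protocol 5.3.5). The follow-up scans are done in all subjects and read centrally. If the SAP is programmed as written, the report will give the proportion of each group with a large cyst on treatment, but no comparable proportion after stopping. A reader could not tell from the tables whether cysts seen at Month 6 had gone, or whether new ones had appeared.

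**Working it through.** There is no power, alpha or rate figure to reproduce. The check is a comparison of texts and a count of visits.

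1. **Scheduled post-baseline ultrasounds** (Protocol 5.3.1.1, Appendix C): 2 on treatment + 2 in follow-up = 4.

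2. **Visits in the planned cyst table.** The protocol's wording covers 4 of 4. SAP 12.7.1 covers Treatment Months 3 and 6, so 2 of 4. The gap is 4 − 2 = 2 visits, and 2/4 = 50%.

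3. **Could the SAP's period rule pull follow-up scans into the treatment table?** SAP 7.4.1 counts ultrasound up to 28 days after the last dose as Treatment Period data. Take the follow-up visits at the SAP's nominal Study End Days, 84 and 168, with the windows in Protocol Table 1:
   - Month 3, general follow-up window of ±7 days: earliest day 84 − 7 = 77.
   - Month 6, ultrasound window of −15 or +4 days: earliest day 168 − 15 = 153.

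   Both exceed 28, so neither scheduled follow-up scan enters the treatment table. Only an early or unscheduled scan could.

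4. **Could the adverse-event tables stand in?** Treatment-emergent events stop at 30 days after the last dose. A cyst first found at a scheduled follow-up scan, and dated to that scan, falls at day 77 or later and is a Post-Treatment event. SAP 12.2.1 tabulates those by system organ class and preferred term, for all events and for serious events. A cyst reaches those tables only if the investigator considers it clinically significant, so they do not count all cysts above the size limits.

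5. **Could the listing stand in?** It identifies subjects and results. It gives no denominator and no percentage by group.

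6. **Are the tools for a follow-up table already in the SAP?** Yes. Table 5 defines TAU/TVU windows: Post-Treatment Month 3 is > 28 to ≤ 126 days, Month 6 is > 126 to ≤ 210 days, and Months 7–12 is > 210 days. Section 12.1 fixes the denominator by leaving out subjects with no evaluation at a visit. Section 12.7.1 already says how several cysts in one subject are handled.

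7. **Special-interest search.** The categories in Protocol 3.2.2 are mood disorders, cutaneous events, hot flush, ovarian-related events, BMD decrease and fractures, uterine bleeding, and serum lipids. Each has a corresponding row in Appendix M except the ovarian one. The nearest row, endometrial safety, searches neoplasms of the uterus and fallopian tube and premalignant reproductive disorders.

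**The case against.** **Follow-up cysts are not ignored.** They are noted in both periods, and subjects with significant findings are listed without a period limit. Any ovarian event reported as an adverse event has a count and percentage by group under its preferred term. This stands, and it is why a reader who infers that ovarian harm is under-reported would go too far. The documents give no post-treatment cyst rate and no sign of an excess. What they show is a missing summary by group.

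**SAP 12.7 may already cover follow-up.** Ovarian cysts are one of its two subsections, and it names Follow-up Months 3 and 6. But it promises values and changes from baseline, which suit continuous measures, and the specific sentence in 12.7.1 limits the count. At best the two sections are unclear together.

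**The limit may be a slip.** SAP 12.7.2 applies the same closing phrase to endometrial-thickness categories that it has just said span both periods. That makes a drafting error likely, so the text does not support reading the cyst limit as a deliberate omission. A slip still needs correcting before tables are programmed.

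**The special-interest premise is soft.** Protocol 3.2.2 describes the elagolix programme in general. The operative Section 6.1.1.3 gives as examples "rash/hypersensitivity, fracture, neuro-psychiatric (depression, mood swings, etc.), vasomotor symptoms (hot flush, night sweats) or serious adverse events", with nothing ovarian. Those are examples rather than a closed list, so they do not cancel 3.2.2, but they do not require an ovarian search either. The Appendix M table was also read from a disordered page, and the contents of its custom queries are not given, so its silence calls for some caution. This point is therefore secondary.

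**Solid lesions.** The protocol's ultrasound list includes "Solid ovarian lesions > 1.5 cm longest diameter", and no SAP section analyses them. A reader might call this a SAP departure. It is not, because Protocol 8.1.8.7 plans tables for the two cyst types only. An at-any-time row would likewise go beyond what the protocol plans.

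**Conclusion.** The mismatch is real. SAP 12.7.1 drops the by-group count and percentage of large ovarian cysts at 2 of 4 scheduled post-baseline ultrasounds, and Protocol 8.1.8.7 plans it at all of them. The listing, the general imaging summary and the adverse-event tables do not restore a rate. The right description is that post-treatment ovarian findings are incompletely summarised by group.

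The effect on any reported number cannot be sized, because the documents contain no follow-up cyst counts. The 50% is a share of visits, not of events or subjects. The conclusion assumes that the protocol's reference to each time point includes the follow-up scans it schedules, that the specific wording of SAP 12.7.1 governs over the general wording of 12.7, and that follow-up scans fall near their nominal days.

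The absent ovarian search in Appendix M is a lesser inconsistency with Protocol 3.2.2. The point concerns reporting only. It does not touch the cyst size limits, the investigator's judgement or the care of subjects.

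**What to change.** **Main change.** In SAP 12.7.1, reword the end of the count sentence so that it covers relevant visits in both the Treatment and the Post-Treatment Follow-up Periods, with follow-up scans assigned by Table 5. This matches Protocol 8.1.8.7 and removes the ambiguity with SAP 12.7.

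**Secondary change.** Reconcile Protocol 3.2.2 with Appendix M by adding an ovarian row with a prespecified term list. Under SAP 12.2.1 the Appendix M summary is planned for treatment-emergent events only, so this row would not fill the follow-up gap unless it were also run on Post-Treatment events. Protocol 8.1.8.2 points that way, since it says Post-Treatment events are summarised similarly to treatment-emergent ones.

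**Optional.** A listing of solid lesions > 1.5 cm. The protocol does not plan a table for them.

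**Cost.** A SAP wording change and a few more table rows from scans and events already collected. No added procedures or visits.
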